## 6.9 Estimated Time Needed to Select Required Number of Subjects

## 7 TREATMENT AND EVALUATION OF ENDPOINTS

### 7.1 Eligibility Committee Review

The EC must confirm the following and determine in which cohort the patient will be placed:

- Tricuspid valve leaflet anatomy is amenable to TriClip™ implantation
- Subject is on optimal medical therapy for both drug and device regimen for any cardiac conditions, per applicable standards.
  - Optimized medical therapy for treatment of TR (e.g. diuretics)
  - Medical and/or device therapy, for mitral regurgitation, atrial fibrillation, coronary artery disease and heart failure

Confirmation of the above eligibility review will be documented.

### 7.2 Roll-in Subjects

The decision to identify a subject as a roll-in will depend on the level of experience of the Implanter with the device. Roll-in subjects will be designated by the Sponsor as such prior to treatment and will not undergo randomization. An implanter may perform **up to 3** roll-in procedures prior to beginning the randomization phase of the trial based on the following criteria:

- Implanters that do not have prior experience with the TriClip™ device OR that have not performed a TriClip™ procedure in the prior 12 months may perform up to 3 roll-in procedures upon approval from the Sponsor

The site must receive authorization from the Sponsor to enroll each roll-in case.

### 7.3 Baseline

#### 7.3.1 Baseline Clinical Assessments

Baseline visit must be performed within 14-days after eligibility has been confirmed by the EC.

**Baseline assessments may occur on the day of treatment but prior to randomization (for randomized subjects):**

- Baseline TTE imaging must be obtained. If screening TTE imaging was performed within 14 days, then screening images may be used as baseline.
- A physical exam including an assessment of subject's cardiac status and vital signs measures must be completed.
- Blood tests performed.
- Concomitant cardiovascular medications must be documented.
- A 12-lead ECG must be performed.

## **TRILUMINATE Pivotal CIP** (Version F)

- Site must reassess subject eligibility and reconfirm that the subject meets eligibility criteria. If there has been significant change in subject's overall condition (i.e. due to recent MI, stroke, etc.), it may be necessary to update assessments completed during the screening process, such as TTE, etc.
- If site is participating in the imaging sub-study, subject must undergo an MRI and CT.
- A standardized script will be used when administering the following assessments:
  - KCCQ and SF-36 QoL questionnaires must be completed by the subject; Note: To minimize bias and undue influence, the QoL questionnaires will be completed by the subject, unless the subject is unable to complete the questionnaire on their own (in such cases a note to file must be completed to document the inability of subject to complete the questionnaire).
  - The 6-Minute Walk Test (6MWT) must be administered according to the ATS Statement: Guidelines for the Six-Minute Walk Test, Official Statement of the American Thoracic Society, approved March 2002 (See APPENDIX XIII: 6 Minute Walk Test Guidelines).
  - An assessment of NYHA Functional Class must be completed.

### **7.4 Randomization**

Randomization shall occur within 14-days after eligibility has been confirmed by the EC. Randomization may occur on the day of treatment, but only after baseline assessments have been completed.

For a subject in the randomized arm, the subject will be randomized in a 1:1 ratio between the Device Group or the Control Group according to a computer-generated randomization scheme accessed via the electronic data capture (EDC) system used for data submission.

Subjects will either be assigned the Device Group or the Control Group. Subjects who are randomized to the Device Group must be scheduled for the index procedure within 14 days.

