### **7.6 Index Procedure (Roll-In, Device Group and Single-arm Cohort)**

The index procedure must be performed within 0 to 14 days after randomization (baseline visit for Single- cohort and Roll-in cohort). If complications arise during the procedure, it may be necessary to convert to an open surgical procedure. Emergency surgical back-up should be available as per the institution's standard procedures.

The Sponsor will be available to provide technical support to answer questions regarding the function and operation of the TriClip™ System. Refer to the IFU for specific instruction on the use TriClip™ device, including handling requirements, preparation for use and precautions.

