### 7.6.2 Pre-Procedure

#### 7.6.2.1 Pre-Procedure Anticoagulation/Antiplatelet Therapy

Perform pre-procedure anticoagulation/antiplatelet therapy according to institution standard of care for transcatheter cardiac procedures. Otherwise, perform anticoagulation/antiplatelet therapy according to the recommended therapy in this section.

Discontinue the use of warfarin for at least three (3) days prior to the scheduled TriClip™ procedure and it is suggested that the international normalized ratio (INR) is  $\leq 1.7$  prior to the TriClip™ procedure. Similarly, discontinue dabigatran or factor Xa inhibitors medications for a sufficient duration to ensure restoration of normal coagulation, or per institution standard of care. Subjects may be treated with heparin during this period at the treating physician's discretion. If heparin is used, it should be discontinued  $\geq 8$  hours prior to the TriClip™ procedure for subcutaneous low molecular weight heparin (LMWH) and  $\geq 4$  hours prior to the TriClip™ procedure for intravenous unfractionated heparin (UFH).

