#### 7.6.2.2 Clopidogrel

A loading dose of clopidogrel ( $\geq 300$  mg) is recommended within 24 hours prior to the procedure (6-24 hours prior if possible) or immediately following the procedure.

**Note:** A loading dose of clopidogrel may be considered even if the patient is taking clopidogrel on a daily basis either at home or in the hospital, as long as no other clopidogrel loading dose has been given within 24 hours. However, clopidogrel use is optional and its use is left to the discretion of the investigator.

Aspirin may also be used at operator discretion. If aspirin is to be used, a loading dose of 325 mg acetylsalicylic acid (ASA) may be administered either pre- or immediately post- TriClip™ procedure.

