## **7.9 “Treatment” Visit (Control Group)**

The “Treatment” visit in the Control group must occur between 0 and 14 days after randomization. At the “Treatment” visit, Control group subjects will be seen by the HF specialist investigator, and will undergo a physical exam, including vital signs, cardiac health status and evaluation of heart failure medications.

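### Randomization may fall on the procedure day, but the default preparation stops warfarin at least 3 days earlier, so the stop can begin before allocation is known and reach subjects who become Controls

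*Protocol*

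**What the plan says.** The timing rules are in the Protocol:

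- Section 7.3.1: "Baseline assessments may occur on the day of treatment but prior to randomization".
- Section 7.4: "Randomization may occur on the day of treatment, but only after baseline assessments have been completed". Allocation is 1:1, and those assigned to Device are then to be scheduled for the procedure within 14 days.
- Section 7.6: "The index procedure must be performed within 0 to 14 days after randomization". Section 7.9 gives Controls the same window: the Treatment "visit in the Control group must occur between 0 and 14 days after randomization".

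The preparation rule is in Section 7.6.2.1. It puts the institution's own practice first. Where that is not used, the recommended therapy applies: "Discontinue the use of warfarin for at least three (3) days prior to the scheduled TriClip™ procedure". Dabigatran and factor Xa inhibitors are also to be stopped ahead of time, without a stated number of days. Heparin may be given in the interval if the treating physician chooses. Section 7.6 as a whole is headed for Roll-in, Device and Single-arm subjects.

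Three other places bear on Controls. Section 4 has both groups stay on their medications unless the physician judges a change necessary. Section 7.7 asks that Control medication be changed only where there is a clinical reason, and describes the medication advice that follows as being for the device arm. Section 7.8.1.2 tells sites to restart an oral anticoagulant that was interrupted for the procedure, as part of care after the device has been placed.

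**The concern.** A stop of several days before a procedure cannot start on the procedure day. If the subject is also randomized on that day, the stop has to begin while the assignment is still unknown. Some of those subjects will be assigned to Control and will have had an anticoagulant interrupted for a procedure that does not take place.

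What is at stake is mainly the safety of Controls. An interruption made only for the procedure does not fit what Sections 4 and 7.7 say about Control medication. No readable section tells a site what applies to a Control who arrives with the anticoagulant already stopped: the restart text follows device placement, and the Control visit in Section 7.9 mentions heart failure medications only. Section 16.4, on the risks of taking part, discusses transesophageal echocardiography and does not mention such an interruption.

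**Working it through.** There is no planned figure to reproduce. The check is one of timing.

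**Inputs**

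- g = days from randomization to procedure. Permitted values are 0 to 14 (Section 7.6).
- s = days the anticoagulant is stopped before the procedure. For warfarin under the default, s is at least 3 (Section 7.6.2.1). For other oral anticoagulants s is not stated. Under an institutional standard s is whatever that standard sets.
- Allocation ratio 1:1 (Section 7.4).

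**Rule.** The stop starts s days before the procedure, and allocation becomes known g days before it. The stop therefore precedes allocation when g < s.

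**Warfarin default, s = 3**

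| g (days) | Stop relative to allocation |
|---|---|
| 0 | starts 3 days before |
| 1 | starts 2 days before |
| 2 | starts 1 day before |
| 3 | can start on the day of randomization |
| 4 to 14 | can start after randomization |

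Of the 15 permitted values of g, 3 give an overlap and 12 do not. This counts calendar options, not subjects: the documents do not say how often each gap is used. A stop longer than 3 days widens the overlap, and a practice with no interruption (s = 0) removes it.

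**Who is reached.** If n subjects have the stop begun before allocation, 1:1 allocation gives an expected n × 1/2 Controls.

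**Why n is unknown.** Two fractions would be needed: the share of subjects with g < s, and the share of those taking an anticoagulant that is stopped. The documents give neither. The nearest figure is atrial fibrillation in 91.8% of the earlier TriClip cohort (Section 2.1.4). That suggests anticoagulant use may be common, but it is not a rate of use, and it comes from another study.

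**Is the link made elsewhere?** No readable section limits short gaps to subjects who need no advance change, or says which step comes first. SAP Section 1.5 on randomization is blacked out and cannot be judged. The sections of the Protocol on baseline, randomization, procedure and discharge that sites would follow are readable.

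**The case against.** The strongest reply is that nothing forces the overlap. Same-day randomization is optional. A site can randomize, then stop warfarin, then treat, all within 14 days, and comply with every section. The 3-day stop is a recommendation that yields to institutional practice. Section 7.6 is not addressed to Controls, and Section 7.4 speaks of scheduling the procedure for subjects already assigned to Device, which suggests assignment first and preparation second. A site that stops an anticoagulant before assignment would be choosing its own workflow.

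Most of this stands, and it limits the point. A reader might infer that the sections cannot both be followed, or that the plan orders withdrawal in Controls. Neither is so. What remains is that the Protocol expressly permits short gaps, attaches no condition to them, and gives no sequence. Deferring to institutional practice may change the length of the stop, but any practice that interrupts for longer than the gap to the procedure creates the same overlap.

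Two further readings are tempting and not supported.

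- *The clopidogrel loading dose raises the same problem.* Section 7.6.2.2 makes clopidogrel optional and allows the loading dose straight after the procedure, and Section 7.8.1.2 repeats that it may be given afterwards. Nothing requires it before allocation.
- *The comparison is biased against Control.* A stop that begins before allocation is shared by both arms, including its effect on baseline medication and laboratory values. Follow-up runs from the Treatment visit (Protocol Section 9.1.1; SAP Section 2.1.1). Stroke and bleeding are not components of the primary endpoint (Protocol Section 5.1.1). The 30-day major adverse event test is a one-group test in the Attempted Procedure population (SAP Section 2.3.1.2.2), so Control harms do not enter it. A route through later deaths is conceivable, but nothing in the documents shows it or gives it a size.

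**Conclusion.** The point holds as a gap in sequence. Under the warfarin default, randomization 0 to 2 days before the procedure means the stop begins before assignment is known, and about half of those prepared this way would be Controls. For other anticoagulants and institutional practices the same holds whenever the gap is shorter than the stop. This sits badly with Sections 4 and 7.7, and the restart text does not reach these subjects.

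The conclusion rests on two conditions: that some sites use the short gaps, and that some subjects at those sites take an anticoagulant that is interrupted for the procedure. The number of Controls affected cannot be derived, and it is zero if either condition fails. A reader might try to size it from the approximately 225 Controls. With purely assumed shares of 10% to 50% randomized on the planned treatment day, and 20% to 60% of those on warfarin under the default, the result runs from 225 × 0.10 × 0.20 = 4.5 to 225 × 0.50 × 0.60 = 67.5. That fifteen-fold spread comes entirely from the assumptions and should not be used as an estimate.

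It is a safety clarification for Controls, worth making because it is cheap. It is not a fault in the analysis.

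**What to change.** Reconcile Protocol Sections 7.3.1, 7.4 and 7.6 with Section 7.6.2.1, so that the permitted randomization timing does not require a procedure-driven anticoagulant change before allocation is known. One sentence on sequence in Section 7.4 would do it. It should cover every gap shorter than the stop, including 1 and 2 days, and not the same-day case alone. The existing windows of 0 to 14 days for the procedure and for the Control visit already leave room, so no visit window has to change.

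The clinical content of Section 7.6.2.1, and what applies to a Control whose anticoagulant was already stopped, are for the sponsor to settle. This review takes no position on either.

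The cost is a short Protocol amendment, and some sites would lose the single-visit workflow for some subjects.

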### **7.5 Blinding**

See **Section 4.2.3** for blinding regarding administration of assessments.

### **7.6 Index Procedure (Roll-In, Device Group and Single-arm Cohort)**

The index procedure must be performed within 0 to 14 days after randomization (baseline visit for Single- cohort and Roll-in cohort). If complications arise during the procedure, it may be necessary to convert to an open surgical procedure. Emergency surgical back-up should be available as per the institution's standard procedures.

The Sponsor will be available to provide technical support to answer questions regarding the function and operation of the TriClip™ System. Refer to the IFU for specific instruction on the use TriClip™ device, including handling requirements, preparation for use and precautions.

#### **7.6.1 Subject Preparation**

Subjects will be prepared for the procedure as per the institution's standard practice for a percutaneous procedure and TEE.

## TRILUMINATE Pivotal CIP (Version F)

**Note:** Prior to performing the procedure, all Investigators must also undergo documented training by the Sponsor on the TriClip™ System and the CIP. In addition, all Investigators must read and understand the IFU that accompanies the Device.

Femoral vein catheterization will be completed in accordance with the IFU.

### 7.6.2 Pre-Procedure

#### 7.6.2.1 Pre-Procedure Anticoagulation/Antiplatelet Therapy

Perform pre-procedure anticoagulation/antiplatelet therapy according to institution standard of care for transcatheter cardiac procedures. Otherwise, perform anticoagulation/antiplatelet therapy according to the recommended therapy in this section.

Discontinue the use of warfarin for at least three (3) days prior to the scheduled TriClip™ procedure and it is suggested that the international normalized ratio (INR) is  $\leq 1.7$  prior to the TriClip™ procedure. Similarly, discontinue dabigatran or factor Xa inhibitors medications for a sufficient duration to ensure restoration of normal coagulation, or per institution standard of care. Subjects may be treated with heparin during this period at the treating physician's discretion. If heparin is used, it should be discontinued  $\geq 8$  hours prior to the TriClip™ procedure for subcutaneous low molecular weight heparin (LMWH) and  $\geq 4$  hours prior to the TriClip™ procedure for intravenous unfractionated heparin (UFH).

#### 7.6.2.2 Clopidogrel

A loading dose of clopidogrel ( $\geq 300$  mg) is recommended within 24 hours prior to the procedure (6-24 hours prior if possible) or immediately following the procedure.

**Note:** A loading dose of clopidogrel may be considered even if the patient is taking clopidogrel on a daily basis either at home or in the hospital, as long as no other clopidogrel loading dose has been given within 24 hours. However, clopidogrel use is optional and its use is left to the discretion of the investigator.

Aspirin may also be used at operator discretion. If aspirin is to be used, a loading dose of 325 mg acetylsalicylic acid (ASA) may be administered either pre- or immediately post- TriClip™ procedure.

#### 7.6.2.3 Antibiotic Therapy

It is recommended to administer a single dose of intravenous broad spectrum antibiotics approximately one hour prior to initiation of the procedure. The type, dosage and timing of antibiotic is at the Investigator's discretion or institution's standard of care.

#### 7.6.2.4 Pre-procedure TEE Imaging

Prior to the TriClip™ procedure, Device group and roll-in subjects must be assessed to ensure there is no significant change in subject's overall condition (e.g., stroke, MI, active infection, endocarditis, hemodynamic instability, etc. post-randomization) that would preclude treatment. If the subject has experienced any significant change that would preclude treatment, the subject must be treated and rescheduled for the TriClip™ procedure as soon as possible. Subjects are required to complete an additional transesophageal (TEE) echocardiogram study within **3 days prior to the procedure** to rule out the presence of intracardiac mass, thrombus or vegetation. This echocardiogram may be performed immediately preceding initiation of the

Study Document No: ABT-CIP-10249

Study Name: TRILUMINATE Pivotal

**CONFIDENTIAL:** May not be reproduced outside of Abbott without written permission from Document Control. This is a quality record which will be retained per the local retention policy.

## TRILUMINATE Pivotal CIP (Version F)

TriClip™ procedure. **This echocardiogram will not be submitted to the ECL.** If an intracardiac mass, thrombus or vegetation or other change in echocardiographic eligibility is identified in the TEE performed immediately preceding the procedure, the procedure should be postponed until the change can be carefully evaluated by site and sponsor. If a thrombus is identified, the subject should be pharmacologically treated to resolve the thrombus and, if successful, the subject should be reassessed as soon as possible to undergo the TriClip™ procedure. Such subjects will be considered enrolled even if they do not undergo the TriClip™ procedure.

### 7.6.2.5 Pre-procedure ECG and Physical Exam

A 12-lead ECG and physical exam must be performed within 24 hours prior to the procedure.

### 7.6.2.6 Activated Clotting Time

Prior to the TriClip™ procedure, baseline activated clotting time (ACT) will be determined following femoral vein puncture for the TriClip™ procedure. ACT and heparin administration (or alternative anticoagulation therapy, e.g., bivalirudin) should be recorded.

### 7.6.2.7 Procedural Anticoagulation Therapy

Following femoral vein puncture, administer intravenous heparin (or alternative anticoagulation therapy, e.g., bivalirudin) in accordance with standard hospital practice. Maintain an ACT (activated clotting time) of > 250 seconds throughout the procedure. Low molecular weight heparin and fondaparinux may not be used for procedural anticoagulation.

## 7.6.3 TriClip™ Device Placement Procedure

Please refer to IFU including storage and handling requirements, preparation for use, pre-use checks of safety and performance, and precautions to be taken after use. All Investigators must read and understand the IFU that accompanies the Device.

Femoral vein catheterization will be completed in accordance with the IFU.

The Steerable Guide Catheter (Guide) is inserted into the femoral vein. Fluoroscopic and echocardiographic (2D and/or 3D-TEE) guidance will be used during the procedure to visualize the device, vasculature and cardiac/valve anatomy. See **Appendix XIV: Monitoring Exposure to Ionizing Radiation** for requirements for training and data gathering on ionizing radiation required per this protocol. For subjects with renal dysfunction, intravenous contrast should not be used during the procedure unless absolutely necessary.

The Guide is positioned in the Inferior Vena Cava/Right Atrium (IVC/RA) and the TriClip™ Delivery System is inserted into the Guide and properly positioned over the tricuspid valve. The TriClip™ Delivery Catheter is advanced until the TriClip™ emerges from the tip of the Guide into the right atrium. Manipulations of the catheter tip (via the control knobs on the handles) will continue in the right atrium until the Clip is properly oriented perpendicular to the line of coaptation of the tricuspid valve leaflets. The Clip is opened and advanced across the tricuspid valve into the ventricle then pulled back to grasp the leaflets. 2- and/or 3-dimensional echocardiography and color flow Doppler are used to evaluate leaflet insertion, Clip position and TR severity. If the Clip is not positioned properly or TR has not been adequately reduced, additional grasping may be attempted and the Clip may be inverted and retracted into the right atrium as required for additional grasping attempts. When placement is successful, the Clip is

## **TRILUMINATE Pivotal CIP** (Version F)

closed and deployed from the Delivery Catheter. The catheters are then removed from the subject.

If placement of one Clip does not result in reduction in TR to a level deemed acceptable by the operator, then additional Clip(s) may be placed to further reduce TR. The Investigator should determine if there is adequate tricuspid valve orifice area to accommodate the additional Clip(s) without creating tricuspid stenosis. A maximum of four (4) Clips will be allowed to be implanted in subjects enrolled in this trial. However, a fifth Clip may be used in the special circumstance if a previous Clip has detached from one leaflet or to stabilize excessive mobility of a previous Clip.

Procedural echocardiograms (TTE and TEE) may be collected immediately post-procedure by the site. Procedural echocardiographic images do not need to be submitted to the ECL.

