### 5.1.3 Descriptive Endpoints

The following descriptive endpoints will be assessed and reported:

- Technical Success at exit from procedure room: Alive with successful access, delivery and retrieval of the device delivery system, and deployment and correct positioning of a Clip, and no need for additional unplanned or emergency surgery or re-intervention related to the device or access procedure
- Device Success at 30-day post-procedure: Alive with original intended Clip(s) in place, and no additional surgical or interventional procedures related to access or device since completion of the original procedure, and intended performance of the Clip(s) (i.e.  $\geq 1$  grade improvement in TR severity, no embolization, single leaflet device attachment, absence of para-device complications)
- Procedural Success at 30-day post-procedure: Device success, and no device or procedure related SAE
- Incidence of peripheral edema requiring hospitalization at 12 months, and annually through 24, 36, 48, and 60 months

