### **7.6.4 Post-Implant**

Post-implant imaging will be used to confirm any occurrence(s) of worsening of TR severity, tricuspid valve and leaflet condition, and any evidence of device embolization, Single Leaflet Device Attachment (SLDA), bleeding, perforation, etc. Treatments for these will be per physicians' discretion. Final TTE and TEE echocardiograms may be acquired and saved by the site.

Immediately following the TriClip™ procedure, heparin (or alternative anticoagulation therapy, e.g., bivalirudin) should be discontinued and the ACT should be monitored in accordance with hospital protocols. Vascular sheaths should be removed according to usual hospital practice.

Post- TriClip™ procedure anticoagulation is recommended per the Investigator's discretion or as described in Section 7.7.3.

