### **SINGLE LEAFLET DEVICE ATTACHMENT (SLDA)**

Defined as unilateral TriClip™ detachment from one leaflet as assessed by the study site and confirmed by the ECL. Reasons for TriClip™ Detachment include leaflet tearing, TriClip™ unlocking, TriClip™ fracture or inadequate TriClip™ placement. Not included are any fractures or other failures of the TriClip™ that do not result in TriClip™ detachment from one or both leaflets.

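### A single leaflet device attachment (SLDA) that is seen at the procedure and gone before the discharge TTE has no required image on which the echo core lab can confirm it

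*Protocol*

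**What the plan says.** **Definition.** The SLDA entry in Protocol Appendix II reads: "Defined as unilateral TriClip™ detachment from one leaflet as assessed by the study site and confirmed by the ECL". The Appendix II entry on non-elective cardiovascular surgery repeats the core-lab condition where it names SLDA as an example. Device embolization, in the same appendix, needs only the site's assessment.

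**Procedure.** Section 7.6.4 has the site use post-implant imaging to look for "any evidence of device embolization, Single Leaflet Device Attachment (SLDA), bleeding, perforation, etc". Section 7.6.3 foresees detachment during the procedure, since "a fifth Clip may be used in the special circumstance if a previous Clip has detached from one leaflet".

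**Images.** Section 7.6.3 says "Procedural echocardiographic images do not need to be submitted to the ECL". Section 7.6.4 adds: "Final TTE and TEE echocardiograms may be acquired and saved by the site". The TEE required within 3 days before the procedure is also not sent to the ECL (section 7.6.2.4).

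**Later echoes.** A TTE is required more than 16 hours after the procedure and no later than the day of discharge (section 7.8), and again at every follow-up visit (section 7.10.2). Section 4.2.5 makes the ECL responsible for echo analyses at all visits.

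**Use of SLDA.** Device Success at 30 days lists, as part of intended Clip performance, "no embolization, single leaflet device attachment, absence of para-device complications". Procedural Success is Device Success without a device- or procedure-related SAE. Both are descriptive endpoints in the Randomized cohort (section 5.1.3) and the Single-arm cohort (section 5.2.3). The continued access study uses the same definition (SAP Appendix B.2).

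**The concern.** The plan sets a confirmation test and does not route all the images needed to apply it. Where an SLDA persists, this does no harm, because the ECL reads a later TTE. Where the event is over before that TTE, the only images showing it are those the site need neither save nor send. The site saw the event, but it cannot meet the definition.

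Any resulting error runs one way: the device looks better than what operators saw. What is at stake is the reported SLDA count and two descriptive success rates, in both cohorts and in a continued access study of up to 600 subjects. The trial's primary and powered secondary tests are not at stake.

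**Working it through.** The plan states no SLDA figure that can be read, so there is nothing to reproduce. The check is to follow the images, then the cases, and then to bound the size under stated assumptions.

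**Step 1. Which images must reach the ECL?**

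| Stage | Imaging | To the ECL? |
|---|---|---|
| Within 3 days before the procedure | TEE (7.6.2.4) | No, stated |
| During and just after implant | TTE and TEE, optional to collect and save (7.6.3, 7.6.4) | Not required, not forbidden |
| Before discharge, more than 16 hours after the procedure | TTE (7.8) | Yes, inferred from 4.2.5 and from 7.10.2, which lists discharge among the follow-up intervals |
| 30 days and later visits | TTE (7.10.2, Table 1) | Yes (4.2.5) |
| Before tricuspid valve surgery | TTE within the preceding 90 days (7.12) | Yes, but it may predate the implant |

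No image taken between implant and the discharge TTE is required to reach the ECL.

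**Step 2. What happens to each kind of SLDA?**

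| SLDA course | Required ECL image showing it? | SLDA count | Device Success |
|---|---|---|---|
| Still visible at discharge or later | Yes | Counted | Counted as a failure |
| Corrected before the discharge TTE and not evident afterwards | No | Can be lost | Can be recorded as a success |
| Operated on before the discharge TTE | No; the pre-surgery TTE may be older than the implant | Can be lost | Normally fails anyway, on the clause excluding later device-related surgery |
| Fatal before the discharge TTE | No | Can be lost | Fails anyway, because the subject is not alive |

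The surgery row is possible in time. Appendix II defines non-elective surgery as required within 24 hours of onset of the event, while the discharge TTE falls after hour 16 and may be later.

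Device Success is therefore exposed mainly through the corrected cases. Its clause on additional procedures counts only those after the original procedure ended, so a further Clip placed in the same session does not trigger it. Procedural Success is exposed in the same cases, unless a device- or procedure-related SAE was also recorded.

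**Step 3. How large could it be?** Two inputs are assumed because the readable text gives neither: the SLDA rate r (2%, 5%, 10%) and the share s visible only on procedural images (0% to 50%).

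Unconfirmed subjects = N × r × s; percentage points = 100 × r × s.

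N is 175 (Device arm, SAP 2.4.1.2.2), 225 (Device group, Protocol Summary) or 200 (maximum of the Single-arm cohort). The cohorts stay separate because SAP 3.5 summarises them separately.

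| r | N = 175 | N = 225 | N = 200 | Points |
|---|---|---|---|---|
| 2% | 0 to 1.8 | 0 to 2.3 | 0 to 2.0 | 0 to 1.0 |
| 5% | 0 to 4.4 | 0 to 5.6 | 0 to 5.0 | 0 to 2.5 |
| 10% | 0 to 8.8 | 0 to 11.3 | 0 to 10.0 | 0 to 5.0 |

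Example: 175 × 0.05 × 0.50 = 4.4 subjects, and 100 × 0.05 × 0.50 = 2.5 points. With s = 0 every entry is zero. For Device Success the upper ends are ceilings, since they require each unconfirmed subject to meet every other element of the definition.

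**The case against.** The strongest reply is that the ECL has several later chances. TTE is required at discharge and at every follow-up visit, the ECL analyses echoes at all visits, and section 7.10.2 requires Clip integrity to be examined at 30 days, when Device Success is assessed. This stands for any SLDA that persists. Nothing in the documents says that a further Clip hides or reattaches a detached one, or that TTE misses SLDA.

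Second, what operators saw is recorded elsewhere. Sites must report all device deficiencies and malfunctions with no ECL condition (8.3.3), adverse events are collected throughout (8.3.1), and Technical Success looks at unplanned re-intervention on leaving the procedure room. This stands as a safety record. It does not repair the rates: deficiency reports have no stated link to Device or Procedural Success, and the text does not say whether an extra Clip in the same session is a re-intervention.

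Third, submission is not forbidden, the echo protocols (Appendices X and XI) and the SAP's Device Success wording for the two cohorts are redacted, and the ECL and CEC charters are not among the documents. A rule for suspected SLDA may sit there. This also stands, and it limits the point to what the readable text leaves open.

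A reader might go further and infer that SLDA as a whole is under-counted, that it is the main device failure, or that it is always first seen on procedural TEE. The documents say none of these. Section 7.6.4 names post-implant imaging as one place to look. A reader might also infer that the safety endpoint is compromised. Appendix II names SLDA only as an example of a complication that may lead to non-elective surgery, so qualifying surgery can count as a major adverse event whether or not the SLDA was confirmed.

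**Conclusion.** The gap is real but narrow. Two stated rules together leave an SLDA that is seen at the procedure, and corrected, operated on or fatal before the discharge TTE, with no required image for confirmation. Such an event can leave the SLDA count; if corrected, it can also leave the subject recorded as a Device or Procedural Success.

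Neither the size nor the existence of an under-count can be derived from the documents. Under the assumed ranges it is 0 to 5 percentage points of device subjects. That rests on an SLDA rate of 2% to 10%, a share of 0% to 50% seen only on procedural images, and Device Success using the Appendix II definition of SLDA. It also takes the discharge TTE to be read by the ECL, which is inferred rather than stated for that visit. No primary or powered secondary endpoint uses SLDA directly. The change is worth making because it is cheap and the possible error runs in one direction.

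**What to change.** In sections 7.6.3 and 7.6.4, require the site to save the procedural and post-implant echo images and submit them to the ECL in two situations: when it suspects SLDA, and when it places a Clip because a previous one detached from one leaflet. Saving must be written in as well as sending, because both are optional now.

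In the SAP, tabulate site-reported SLDA beside ECL-confirmed SLDA, by cohort, and show Device Success under each count.

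Keep ECL confirmation as the main definition. Counting every site report unless the ECL refutes it would give up some of the independent image review that section 4.2.5 relies on to limit bias, and the side-by-side table makes that unnecessary. No treatment rule changes.

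The cost is amended wording, saving and sending a few image sets, a small number of extra reads by the existing ECL, and one more table. If an ECL or CEC charter already requires these images for suspected SLDA, a cross-reference in 7.6.3 would settle the image part.
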